The European Association of Urology (EAU) and American Association of Urology (AUA) guidelines on urolithiasis recommended use of URSL and SWL for treating upper ureteric stones^{5,6}. In the recent years there has been a paradigm shift towards increased use of URSL with decreased SWL use for treating upper urinary tract stones^{7,8}. It has been postulated that URSL for ureteric stones has higher stone free rate compared to SWL with less need for secondary procedures⁹. Also URSL has a more favorable cost-efficiency profile compared to SWL in treating proximal ureteric stones when chosen as the primary treatment modality¹⁰. The EAU guidelines on urolithiasis recommends URSL as first option to treat proximal ureteric stones > 10 mm in maximum dimension and to use antegrade access whenever the collecting system is dilated or the retrograde access is inconvenient⁵. Recently many studies assessed the antegrade access for upper ureteric stones making use of different urological endoscopes available with different percutaneous tract sizes through the kidney according to used endoscope varying between conventional nephroscopes¹¹, semirigid ureteroscopes¹¹, mini nephroscopes¹², flexible nephroscopes¹³ and flexible ureteroscopes⁴ demonstrating superior stone free rate with percutaneous antegrade access with comparable safety profile with retrograde URSL.

2. AIM/ OBJECTIVES (Maximum 300 words)

We aim to assess the efficacy and safety of antegrade URSL in treating upper ureteric stones >10 mm in its maximum dimension and impacted upper ureteric stones irrespective of its size in comparison to retrograde URSL and evaluate feasibility, adverse events, hospital stay and cost benefit of both techniques.

3. METHODOLOGY:

Patients and Methods/ Subjects and Methods/ Material and Methods (Maximum 1000 words)

“References may be needed”

- **Type of Study**

Randomized prospective study

- **Study Setting**

- Department of urology, Ain Shams University

- **Study Period**

- 4 years

- **Study Population**

- Inclusion Criteria:

- Age > 18 years

- Upper ureteric stones > 10 mm

- Impacted upper ureteric stones defined by non movable stone on CTUT for 1 month or intraoperative failure to pass a guidewire beyond the stone

- Exclusion Criteria:

- Unresolved urinary tract infection

- Uncorrected coagulopathy

- pregnancy

- Anatomical abnormalities of the urinary system as horse shoe kidney, pelvic ectopic kidney and ureteric strictures.

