- Severe orthopedic malformation hindering prone position or antegrade ureteric access as Kyphosis, scoliosis.

- Pediatric age groups < 18 years

- Ureteric Stent in place

- Concurrent renal stones
- Bladder cancer, upper urothelial tumors and renal tumors.

- **Sampling Method**

Randomization will be done by statistician.

- **Sample Size**

50 patients in either arm, aborted cases will be included.

- **Ethical Considerations**

Patients will be asked to provide a signed written informed consent

- **Study Procedures:**

- **Pre operative work up:**

- Patients will undergo detailed history taking, physical examination.

- **Laboratory work-up:**

- Complete blood count (CBC)
- Coagulation profile
- Kidney function tests
- Liver function tests
- Urine analysis
- Urine culture and sensitivity

- **Imaging:**

- Patients will undergo plain computed tomography of the urinary tract (CTUT) to be eligible for diagnosis of upper ureteric stone. Upper ureteric stone definition will be the distance from pelviureteric junction to

the proximal border of sacroiliac junction. Impacted stones will be defined as non movable stones for 1 month on CTUT

- Signed informed consent

- Patients who fulfill inclusion criteria will be randomized into 2 groups:
Antegrade URSL(A-group), retrograde URSL(B-group).

- Operative procedure:

Antegrade URSL- Group A:

- 1- All patients will be anesthetized by general anesthesia.
- 2- The patient will be in lithotomy position, cystoscopy will be done, guide wire will be passed to the ureter to bypass the ureteric stone and advanced to the collecting system of the kidney, ureteric catheter (6 Fr, open tip) will pass over the guidewire and an indwelling urethral catheter will be placed in the urinary bladder
- 3- The patient will be placed in prone position, retrograde pyelography via ureteric catheter will be done, puncture of the collecting system will be done through upper or middle calyx using 18-gauge percutaneous puncture needle guided by fluoroscopy. In case of impacted stones and non passage of guidewire beyond the stone, localization of renal pelvis by 18 gauge Shiba needle in prone position guided by ultrasound will be done then antegrade pyelography will be performed to proceed with calyceal puncture.
- 4- 0.035 inch PTFE J tip guidewire will be introduced through the puncture needle sheath and negotiated into the ureter down to the stone guided by fluoroscopy.

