We used the Statistical Package for Social Sciences (IBM Corp. Released 2019. IBM SPSS Statistics for Windows, Version 29.0. Armonk, NY: IBM Corp.) for data analysis. Descriptive statistics were presented as mean \pm standard deviation (SD) or as numbers and percentages. Normality was tested using the Shapiro-Wilk test. Data that were normally distributed were presented as mean \pm SD, while non-normally distributed data were presented as median and 95% confidence intervals (CIs).

The chi-square (χ^2) test assessed relationships between categorical variables. For parametric variables, the student's t-test was applied to compare means between study groups, while the Mann-Whitney U test was used to compare medians for variables such as stone size and hospital stay. Fisher's exact test was employed for categorical variables with expected counts < 5 . Spearman's correlation was used to analyze relationships between non-normally distributed variables. Binary logistic regression was done to illustrate the odds ratio for complications. A P-value < 0.05 was considered statistically significant.

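### With 50 patients per arm, the planned odds ratio for complications has no finite value if either arm has no events, and no fallback estimate is named

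*Combined protocol and SAP*

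**What the plan says.** Under Aim/Objectives, the trial is to assess efficacy and safety and to "evaluate feasibility, adverse events, hospital stay and cost benefit of both techniques". Under Sample Size, the plan sets "50 patients in either arm, aborted cases will be included", without a rate, an effect size or a power. The two arms are "Antegrade URSL(A-group), retrograde URSL(B-group").

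The Statistical analysis section says of safety: "Binary logistic regression was done to illustrate the odds ratio for complications". It does not define the complication outcome (any complication per patient, or each type), list the predictors, name a penalised or exact variant, or say what is reported if an arm has no events. For sparse tables it provides a test only: Fisher's exact "test was employed for categorical variables with expected counts < 5". Categorical data are otherwise described as counts and percentages and compared by chi-square. No risk difference, risk ratio or interval for a difference in proportions is planned.

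**The concern.** In a logistic model with treatment arm as predictor, the maximum-likelihood odds ratio is finite and non-zero only if each arm contains at least one patient with the event and one without. With 50 patients per arm, an uncommon complication can easily leave an arm with none. Software then typically reports a huge or near-zero odds ratio with an unusable interval. Safety is half of the stated aim, and this odds ratio is the only quantity planned to express how far the arms differ on it. Because the outcome is undefined, the model might also be applied to single complication types, where low rates are more plausible than for a composite. Without a rule set in advance, the replacement method would be chosen after the empty cell had been seen.

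**Working it through.** **Inputs.** From the documents: n = 50 per arm (Sample Size) and a logistic odds ratio for complications (Statistical analysis). Assumed, because the documents do not give them: the complication rate per arm, taken from 1% to 20%; treatment arm as the only predictor; an unpenalised fit, which is the natural reading of the unqualified term. The sample size itself cannot be reproduced, because no rate, effect or power accompanies it.

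**Step 1: chance of no finite odds ratio.** For an arm with rate p, the chance of all non-events or all events is q(p) = (1 − p)^50 + p^50; the second term is negligible here. For two arms, P = qA + qB − qA·qB.

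Example at 5% in both arms: 0.95^50 = 0.0769, so P = 2(0.0769) − 0.0769² = 0.148.

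| Rate in both arms | P(no events in a given arm) | P(no finite odds ratio) |
|---|---|---|
| 1% | 60.5% | 84.4% |
| 2% | 36.4% | 59.6% |
| 3% | 21.8% | 38.9% |
| 4% | 13.0% | 24.3% |
| 5% | 7.7% | 14.8% |
| 8% | 1.5% | 3.1% |
| 10% | 0.5% | 1.0% |
| 15% | 0.03% | 0.06% |
| 20% | <0.01% | <0.01% |

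Unequal rates: 2% v 6%, 39.3%; 4% v 10%, 13.4%; 5% v 15%, 7.7%; 10% v 20%, 0.5%. With equal rates, the chance falls below 10% at about 5.8% per arm and below 5% at about 7.1%.

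**Step 2: the same in terms of events seen.** With m events in total and equal risk, the chance that all fall in one arm is 2·C(50,m)/C(100,m) for m ≥ 2: 49.5% for 2 events, 24.2% for 3, 11.8% for 4, 5.6% for 5, 2.7% for 6 and 0.1% for 10.

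**Step 3: added covariates.** None is named, so this is illustrative only. With three assumed covariates (two binary, at 20% and 50% prevalence, and one continuous; 1,000 simulated trials per rate), some coefficient in the model was not finite in about 85% of trials at 2%, 49% at 5%, 15% at 10% and 1% at 20%. That coefficient need not be the treatment effect.

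**Step 4: what the proposed estimates give.** In a treatment-only model the Firth odds ratio equals the 2×2 odds ratio with 0.5 added to every cell. For 0 v 3 events of 50 it is (0.5 × 47.5)/(3.5 × 50.5) = 0.13; for 0 v 5 it is (0.5 × 45.5)/(5.5 × 50.5) = 0.08. Both are finite.

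The risk difference is defined in every case, but its interval method matters. At 0/50 v 0/50 a Wald interval has zero width. The Newcombe interval does not: the Wilson upper limit for 0/50 is 1.96²/(50 + 1.96²) = 3.84/53.84 = 7.1%, giving −7.1% to +7.1%.

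**Step 5: direction of bias.** At true rates of 6% v 2% the log odds ratio is ln[(0.06/0.94)/(0.02/0.98)] = 1.14. Summing over all binomial outcomes with a finite maximum-likelihood estimate, the mean is 0.69, which is below the truth. Summing over all outcomes with 0.5 added to each cell, the Firth mean is 0.98, also pulled toward 1 on the odds-ratio scale, but less so.

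**The case against.** The strongest reply is that the documents give no complication rate, and the result depends on it. If complications means any complication and the rate is 10% or more per arm, a treatment-only odds ratio is finite in about 99% of trials or more. This stands, and it is why the point is conditional. A reader might infer that the planned estimate will often fail; nothing in the documents places the rate in the range of roughly 1% to 4% where that would be true.

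A second reply is that the safety comparison is not lost. Counts and percentages will be shown, and Fisher's exact test covers exactly the sparse case. With 50 per arm, expected counts fall below 5 whenever there are fewer than 10 events in total (10/2 = 5). This also stands. But Fisher's test supplies a p-value, not a size of effect or its uncertainty. The plan thus foresees sparse tables for testing and makes no matching provision for estimation.

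A third reply is that the odds ratio is meant only to illustrate, and that an infinite value at 0/50 is obvious to any reader. That lowers the stakes, but does not supply an estimate.

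A reader might also infer that finite odds ratios from this model are generally exaggerated. Step 5 shows the opposite at 6% v 2%, so general exaggeration is not part of the point.

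**Conclusion.** The point holds in conditional form and is minor. If complications, or single complication types, are uncommon, the only planned safety effect estimate may have no finite value: 60% of trials at 2% per arm, 24% at 4%, 15% at 5%, 3% at 8%, 1% at 10%, and a negligible share well above that. These figures rest on equal assumed rates, treatment arm as the sole predictor, and ordinary maximum likelihood; the last two are inferences from an unqualified sentence.

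The stronger conclusion, that the safety comparison itself fails, is not supported, because the percentages and Fisher's exact test remain. The gap is an estimate and interval that survive an empty cell, together with a definition of the outcome that decides how sparse the data will be. The remedy does not depend on knowing the rate: it changes little when events are common and supplies a finite estimate when they are few.

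**What to change.** Replace the logistic regression sentence in the Statistical analysis section with:

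> The proportion of patients with at least one complication is compared between arms by risk difference with a 95% score (Newcombe or Miettinen-Nurminen) confidence interval, with Fisher's exact test when expected counts are below 5; the odds ratio comes from Firth-penalised logistic regression with treatment arm as the predictor and profile-likelihood confidence limits.

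One of the two score intervals should be picked when the sentence is finalised. The sentence fixes the outcome per patient, names the predictor and leaves no covariate set to be chosen later.

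Cost: one sentence, no extra patients or data. With very few events the penalty pulls the odds ratio toward 1, so the risk difference should be read as the main safety estimate there. The plan names SPSS version 29, and the Firth fit may need an add-on or a second package.
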